Secondary	
- To determine the degree of in-field tumor response at 6, 12, 18 and 24 months following completion of SBRT- To compare progression-free survival, overall survival, local tumor control, and distant metastasis rates over a 2-year follow up period for SBRT plus GC4711 or placebo- To assess durability of in-field complete or partial responses- To determine acute lung toxicity after SBRT + GC4711 compared to SBRT + placebo for early-stage NSCLC- To evaluate the rate of acute and late radiation toxicities for SBRT + GC4711 compared to SBRT + placebo- To assess the relationship between clinical, functional and radiographical lung function changes observed after SBRT 
- Percent reduction of in-field tumor at Months 6, 12, 18 and 24- Number of participants with CR+PR- Number of participants experiencing grade 1 or higher in diffusion capacity of lung for carbon monoxide (DLCO), measured by RTOG scale, at 6-months after the completion of SBRT- Measurement of the following parameters over 12 months after SBRT
- Changes in pulmonary function testing (pulse oximetry [SpO₂], forced vital capacity [FVC], first expiratory volume in the first second [FEV₁], DLCO), clinical and radiological pneumonitis scoring- Reporting of observed adverse events in patients- Late Radiation Toxicities (including clinical and radiographic pneumonitis, esophagitis, pulmonary fibrosis, rib fractures, plexopathy, cardiac and vascular events) up to 12 months following the completion of SBRT- Measurement of the following parameters over 24 months after SBRT
- Progression Free Survival (PFS)- Overall Survival (OS)- Local and regional control- Distant Metastases (DM) rate

OBJECTIVES	ENDPOINTS
	-

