6.2 Stereotactic Body Radiation Therapy (SBRT)

SBRT Dosage, Administration, and Schedule

Patients will be evaluated by the treating radiation oncologist at the local site. Based on location and size of the tumor, dose planning will be determined by clinical appropriateness that balances ablation of the lesion(s) while respecting normal tissue constraints including for ultra-central lesions the volume criterium of the contoured proximal bronchial tree less than 0.03cc =<52.5Gy (Bejzak 2019).

Table 2 Organ Constraints for a 3-Fraction SBRT Regimen

Serial Tissue	Volume (cc)	Volume Max (Gy)	Max Point Dose (Gy) ²	Endpoint (\geq Grade 3)
Esophagus ¹	<5	27.9	32.4	Esophagitis
Brachial Plexus	<3	22	26	Neuropathy
Heart/Pericardium	<15	24	30	Pericarditis
Great vessels	<10	39	45	Aneurysm
Trachea and Large Bronchus ¹	<5	39	43	Impairment of pulmonary toilet
Bronchus smaller airways	<0.5	25.8	30	Stenosis with atelectasis
Rib	<5	40	50	Pain or fracture
Lung (Right & Left)	1500 for males; 950 for females ³	10.8		Basic Lung Function
Lung (Right & Left)			V-11.4Gy<37%	Pneumonitis
Spinal cord	<0.35	15.9	22.5	Myelitis

Abbreviations:

1. Avoid circumferential irradiation

2. “point” defined as 0.035cc or less

3. or one-third of the “native” total organ volume (prior to any resection or volume reducing disease), whichever is greater:

- Exceeding these dose tolerances by more than 2.5% constitutes a minor protocol violation.

- Exceeding these dose tolerances by more than 5% constitutes a major protocol violation.

Table 3 Organ Constraints for a 5-Fraction SBRT Regimen

Serial Tissue	Volume (cc)	Volume Max (Gy)	Max Point Dose (Gy) ²	Endpoint (\geq Grade 3)
Esophagus ¹	<5	32.5	38	Esophagitis
Brachial Plexus	<3	27	32.5	Neuropathy
Heart/Pericardium	<15	32	38	Pericarditis
Great vessels	<10	47	53	Aneurysm
Trachea and Large Bronchus ¹	<5	45	50	Impairment of pulmonary toilet
Bronchus smaller airways	<0.5	32	40	Stenosis with atelectasis
Rib	<5	45	57	Pain or fracture
Lung (Right & Left)	1500 for males; 950 for females ³	12.5		Basic Lung Function
Lung (Right & Left)			V-13.5Gy<37%	Pneumonitis
Spinal cord	<0.35	22	28	Myelitis

Abbreviations:

1. Avoid circumferential irradiation
2. “point” defined as 0.035cc or less
3. or one-third of the “native” total organ volume (prior to any resection or volume reducing disease), whichever is greater:
 - Exceeding these dose tolerances by more than 2.5% constitutes a minor protocol violation.

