7.2 Adverse Events and Serious Adverse Events

The definitions of an AE or SAE can be found in

Appendix 3. The Investigator is responsible for the detection and documentation of events meeting the criteria and definition of an AE or SAE as provided in this protocol. Throughout the study, AEs will be recorded in the source documents and on the appropriate pages of the CRF regardless of whether the AEs are considered related to GC4711/Placebo or SBRT. To avoid confusion, the AE should be recorded in standard medical terminology.

Adverse event(s) will be reported by the participant (or, when appropriate, by a caregiver, surrogate, or the participant's legally authorized representative).

The investigator and any qualified designees are responsible for detecting, documenting, and recording events that meet the definition of an AE or SAE and remain responsible for following up AEs that are serious, considered related to the study intervention or study procedures, or that caused the participant to discontinue the study intervention/study (see Section 5.4).

Time Period and Frequency for Collecting Adverse Events and Serious Adverse Events Information

All adverse events will be collected from the Day 1 dosing through 90 days post-SBRT completion to ensure collection of acute toxicities and up to 12 months for late radiation toxicities. Please see Section 7.4 for the definition of late radiation toxicities.

All SAEs will be recorded and reported to the sponsor or designee immediately and under no circumstance should this exceed 24 hours, as indicated in

Appendix 3. The investigator will submit any updated SAE data to the sponsor within 24 hours of it being available. Specific SAE reporting instructions are provided in a separate manual.

Method of Detecting Adverse Events and Serious Adverse Events

The method of recording, evaluating, and assessing causality of AEs and SAEs and the procedures for completing and transmitting SAE reports are provided in

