7.4 Late Radiotherapy Toxicities

Late radiotherapy toxicities will be collected as per the Schedule of Assessments. Related, late radiation toxicities (Kang 2015) will be collected up to 12 months post SBRT and defined using NCI Common Terminology Criteria for Adverse Events (version 5.0).:

- Grade 1-5 Respiratory, thoracic and mediastinal disorders, including rib fractures
- Grade 1-5 esophagus, and
- Grade 3-5 cardiac events
- Grade 3-5 spinal cord/brachial plexopathy and vascular events

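### Section 7.4 names late rib fractures but not rib pain, and the Phase 2 endpoint in Section 3 does not state the Grade 3-5 floor that Section 7.4 sets for plexus, cardiac and vascular events

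*Combined protocol and SAP*

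**What the plan says.** Section 7.2 sets the first collection window: "All adverse events will be collected from the Day 1 dosing through 90 days post-SBRT completion to ensure collection of acute toxicities". For the period up to 12 months it sends the reader to Section 7.4 for the definition of late radiation toxicity. The synopsis and footnote i of the Schedule of Activities make the same referral.

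Section 7.4 opens with "Related, late radiation toxicities (Kang 2015) will be collected up to 12 months post SBRT" and then gives four items under CTCAE version 5.0:

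- "Grade 1-5 Respiratory, thoracic and mediastinal disorders, including rib fractures"
- esophagus, also Grade 1-5
- "Grade 3-5 cardiac events"
- "Grade 3-5 spinal cord/brachial plexopathy and vascular events"

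There is no category for other events.

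Tables 2 and 3 in Section 6.2 (Stereotactic Body Radiation Therapy) set organ dose constraints and name the toxicity each is meant to prevent. The column heading limits these toxicities to Grade 3 or higher. For the rib the entry is "Pain or fracture".

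The Phase 2 secondary endpoints in Section 3 include late radiation toxicities, with a parenthetical list ending "pulmonary fibrosis, rib fractures, plexopathy, cardiac and vascular events) up to 12 months following the completion of SBRT". No grade is attached. The Phase 1 row names rib fractures but no plexus, cardiac or vascular events. Neither row names rib pain.

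**The concern.** The Section 7.4 list decides what enters the database after Day 90. If an event type is absent from it, sites have no instruction to record that event, and the analysis cannot recover it. The protocol's own radiotherapy planning tables treat severe rib pain as a harm on a par with fracture, yet the late-toxicity definition carries over only the fracture half.

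The grade question is separate. A reader of Section 3 alone would take the late plexopathy, cardiac and vascular counts to have no grade restriction, while the data behind them would contain only Grade 3-5 events. Comparing acute and late radiation toxicity between GC4711 and placebo is a secondary Phase 2 objective, so it should be clear what the late count contains.

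**Working it through.** The plan states no figure on this point, so there is none to reproduce. The check compares texts and adds one labelled illustration.

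**Step 1: is the list closed?** It has four items and no residual category. The synopsis describes one-year monitoring as being for specific late toxicities defined in Section 7.4. Footnote i ends general AE and SAE collection at 90 days. Read together, an event after Day 90 that fits none of the four items is not collected as a late toxicity.

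**Step 2: match each toxicity in Tables 2 and 3 to Section 7.4.**

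| Tissue in Tables 2 and 3 | Toxicity (Grade 3 or higher) | Item in Section 7.4 |
|---|---|---|
| Esophagus | Esophagitis | Esophagus, Grade 1-5 |
| Brachial plexus | Neuropathy | Cord/plexus, Grade 3-5 |
| Heart/pericardium | Pericarditis | Cardiac, Grade 3-5 |
| Great vessels | Aneurysm | Vascular, Grade 3-5 |
| Trachea, bronchi, lung | Airway and lung toxicities | Respiratory class, Grade 1-5 |
| Spinal cord | Myelitis | Cord/plexus, Grade 3-5 |
| Rib | Pain or fracture | Fracture named; pain not named |

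Rib pain is the only toxicity in the tables without a clear match. For heart, vessels, plexus and cord, the Grade 3-5 floor in Section 7.4 agrees with the tables.

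**Step 3: is there another record of late rib pain?** After Day 90, Section 6.1 (Collection of Concomitant Medications) keeps only drugs for respiratory disease or late radiation toxicities, and footnote j only those for late radiation toxicities. A painkiller for rib pain would be recorded only if the pain already counted as a late toxicity, which is the open question.

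**Step 4: compare the grade wording.** Section 3 (Phase 2) gives no grade for plexopathy, cardiac or vascular events. Section 7.4 sets Grade 3-5. Section 8.5 states no threshold for the safety tables.

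**Step 5: illustration of size.** Let r be the proportion of patients with related rib or chest-wall pain that first occurs between Day 90 and Month 12 and is not coded elsewhere. The documents do not give r, so the values below are assumptions. With n = 33 per arm (synopsis), the expected number of uncollected patients is n × r, and the chance of at least one is 1 − (1 − r)^33.

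- r = 2%: 33 × 0.02 = 0.7 patients; 1 − 0.98^33 = 49%
- r = 5%: 33 × 0.05 = 1.7 patients; 1 − 0.95^33 = 82%
- r = 10%: 33 × 0.10 = 3.3 patients; 1 − 0.90^33 = 97%

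These figures cover all grades of such pain. For Grade 3 or higher alone, r would be lower.

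**The case against.** The strongest defence is that Section 7.4 is the definition and Section 3 merely names the subject. Three places in the protocol refer to Section 7.4 for what counts as late toxicity, and Section 3 never says it counts all grades. On that reading the endpoint is whatever Section 7.4 collects, and it can be tabulated. This stands. A reader might infer that the Section 3 endpoint cannot be computed, or that Grade 1-2 cardiac, vascular and plexus events are wrongly dropped. The documents do not support either inference. Section 3 is silent on grade, the floor matches the dose tables, and collecting fewer grades for these classes is a legitimate choice of scope. What remains is that the endpoint text should state the floor.

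On rib pain, the defence has three parts.

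- The tables are planning constraints, not trial endpoints, and they concern Grade 3 or higher. This stands as a limit on grade: they do not support a requirement to collect Grade 1-2 rib pain.
- Table 5 lists pain as acute, not late. This carries little weight. Its late column is mostly abdominal and omits pneumonitis, pulmonary fibrosis and rib fracture, all of which Section 3 counts as late.
- Section 7.4 takes in a whole respiratory and thoracic class, and rib pain might be coded there. This cannot be ruled out, because the CTCAE dictionary is not in the documents. But the protocol found it necessary to name rib fractures, so leaving pain unnamed invites sites to differ.

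A reader might also infer bias between arms, or an artificial fall in event rates from the acute to the late period. Neither is shown. The rule is identical in both blinded arms, the objective compares arms, and no acute-versus-late comparison is planned.

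**Conclusion.** Two limited points hold.

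First, Section 7.4 does not name rib pain, while Tables 2 and 3 treat it at Grade 3 or higher as a rib toxicity alongside fracture. Unless it is coded under the respiratory and thoracic class, related rib or chest-wall pain arising after Day 90 is lost from the late-toxicity endpoint, in both arms alike. This is worth correcting because data not collected cannot be recovered at analysis.

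Second, Section 3 (Phase 2) and Section 7.4 differ in wording on grade for plexopathy, cardiac and vascular events. This needs clarification; it is not a defect in the endpoint. It does not arise in the Phase 1 row, which lists none of these events.

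The size of any under-count of rib pain cannot be derived from the documents. The illustration of about 0.7 to 3.3 patients per arm rests wholly on assumed rates of 2% to 10% for new related pain between Day 90 and Month 12. Applying a full 12-month rate would overstate the loss, because events through Day 90 are collected.

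**What to change.** In Section 7.4, name rib or chest-wall pain beside rib fractures, at least at Grade 3-5 to match Tables 2 and 3. Collecting lower grades is optional.

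In the Phase 2 row of Section 3, add Grade 3-5 (per Section 7.4) after plexopathy, cardiac and vascular events, and label the late-toxicity tables the same way. If acute and late rates for these classes are ever set side by side, apply the Grade 3-5 floor to both periods; the acute data hold all grades, so this needs no extra collection.

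The cost is a few lines of protocol text and a few more adverse-event entries at the existing Month 6 and Month 12 reviews. No visit or test is added.

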7.5 Phase 1 Dose-limiting Toxicities

Safety will be confirmed by the occurrence of dose limiting toxicities (DLTs), which are defined (using the NCI-CTC grading scale) as Grade 3-5 AEs occurring from Day 1 to 30 days post SBRT, and *excluding* the following:

- AEs clearly related to disease progression or intercurrent illness
- Grade 3 fatigue for 7 days or less,
- Grade 3 nausea/vomiting or diarrhea for less than 72 hours with adequate antiemetic and other supportive care
- Grade 3 or higher electrolyte abnormality that lasts up to 72 hours, is not clinically complicated, and resolves spontaneously or responds to conventional medical interventions
- Grade 3 or higher amylase or lipase that is not associated with symptoms or clinical manifestations of pancreatitis
- Hematological grade 3-4 toxicities except for the following:
 - Grade 4 neutropenia lasting >7 days.
 - Grade 3 thrombocytopenia with clinically significant bleeding.
 - Grade 4 anemia and grade 4 thrombocytopenia

Safety will be considered unacceptable in the Phase 1 portion of the study, if a DLT occurs in 2 or more of the first 5 subjects.

In the event of an occurrence of a DLT, the SRC will meet and determine what action should be taken with treatment.

Opening enrollment in the Phase 2 is dependent on the safety outcome (DLT occurrence) in Phase 1.

7.6 Pharmacokinetics (PK) and ECG

PK sampling will be sought from all patients for GC4711 and its two metabolites, GC4752 and GC4757. Blood sampling will be performed along with the ECGs on the days and times indicated in the Schedule of Assessments) and outlined below.

PK Draw	PK draw window	ECG
Pre-dose	- 1 hour from start of infusion	+/- 10 minutes of PK draw (triplicate)
End of Infusion	+ 10 minutes from EOI	+/- 10 minutes of PK draw (triplicate)
24-hour Post dose (Phase 1 only)	Prior to dosing if delivered on next sequential day	+/- 10 minutes of PK draw (single)

A separate PK Manual will be provided.

8 STATISTICAL CONSIDERATIONS

8.1 Sample size

In Phase 1 of the study, 5 patients will be treated with GC4711 in combination with SBRT. Dose limiting toxicity (DLT) is defined in Section 7.5. Safety is considered acceptable and confirmed in the Phase 1 portion of the study, if DLT occurs in no more than one of the first five DLT-evaluable patients.

If acceptable safety in Phase 1 is confirmed, Phase 2 will proceed. Approximately sixty-six (66) participants, randomized 1:1 to GC4711 or placebo, will be recruited for the Phase 2 portion to achieve 60 evaluable subjects, assuming an approximate 9% drop out rate prior to the 90-day timepoint evaluation.

The primary objective in Phase 2 is to estimate the difference in in-field tumor response between GC4711 and placebo through Month 6 following SBRT. Sample size in Phase 2 is selected to provide a reasonably precise estimate of the treatment effect as measured by the width of a two-sided 90% confidence interval around the difference in in-field tumor response as well as to provide other efficacy data that can be used in planning future studies. With 30 patients/arm the half-width of the 90% confidence interval for the difference will be at most 21.2% based on the large sample confidence interval with limits $\pm Z.05 \sqrt{[(p1*(1-p1)/n + p2*(1-p2)/m)]}$ of the point estimate where p1 and p2 are the response rates and n and m the corresponding number of patients in each arm.

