Inclusion and exclusion criteria ^e	X									
Registration/Randomization (Phase 1/Phase 2) ^e	X									
Medical history (includes smoking history)	X									
Demography	X									
Complete PE including height and weight	X								X	
ECOG Performance Status	X								X	
Vital signs ^f	X	X	X	X	X	X				
PK Blood samples ^g		X	X							
12-lead ECG ^h	X	X		X						
AE/SAE review ⁱ		X	X	X	X	X	X	X	X	
Concomitant medications/treatments and smoking review ^j	X	X	X	X	X	X		X	X	X
Survival Status								X	X	X
Serum pregnancy test (WOCBP only)	X									
Serum chemistry panel	X						X			
Complete blood count	X						X		X	
PT/INR, aPTT	X									
PFTs – SpO ₂ , FEV1, FVC and DLCO ^{k, n}	X								X	
CT chest for pneumonitis scoring ^k	X								X	X
CT (chest, abdomen, pelvis) ^k	X								X	X
GC4711/Placebo IV infusion ^l		X	X	X	X ^l	X ^l				
SBRT administration ^m		X	X	X	X ^m	X ^m				

AE = adverse event, BP = blood pressure, CBC = complete blood count, CT = computed tomography, CTCAE = Common Terminology Criteria for Adverse Events, DLCO = diffusion capacity of lung for carbon monoxide, ECG = electrocardiogram, ECOG PS = eastern cooperative oncology group performance status, FEV1 = forced expiratory volume in 1 second, FU = Follow-up, , IV = intravenous, PE = physical examination, PET = positron emission tomography, PFTs = pulmonary function tests, PK = pharmacokinetics, SAE = serious adverse event.

- a Screening evaluations should occur within 21 days of Treatment Day 1, except where otherwise noted
- b The Day 12 visit should occur 7 days after the last dose of SBRT \pm 5 days
- c The 30- and 90- day post SBRT completion visits should occur on or within 7 days after target date and may be performed remotely via telemedicine visits. The Months 6 and 12 post SBRT completion visits should occur \pm 7 days of target date.
- d The Month 18 and 24 post SBRT visits should occur \pm 14 days of target date.
- e Registration/Randomization should occur after all screening assessments are performed, eligibility is confirmed, and within 7 days of the first dose of SBRT. Confirmation of eligibility should include confirmation of diagnosis, histology and exclusion of distant disease by standard practice.
- f BP and HR should be taken prior to each infusion, monitoring possible hypotensive symptoms, please repeat before going from infusion to radiation site.

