4.2 Study Duration for Participants

The study duration for participants is expected to be approximately 25 months. This includes a 21-day screening period, a treatment period of approximately 5-10 days, and long-term follow-up for 24 months. All subjects are evaluated 30 days after SBRT and 6, 12, 18 and 24 months post-SBRT.

If a participant experiences progressive disease prior to 24 months post-SBRT completion, they will continue for survival follow-up until end of study (24 months following the last administration of SBRT). No additional tumor assessments will be required after progression; however, adverse events for long term radiation toxicities will continue through 12 months post SBRT completion and survival follow up will continue through 24 months post SBRT completion.

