4.4 Replacement of Participants

In Phase 1, if a subject is withdrawn from the study prior to completing GC4711/Radiotherapy and 30 days of follow-up without experiencing a DLT prior to withdrawal, an additional subject may be added.

In Phase 2, patients who are randomized but do not receive study drug may be replaced.

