8.3 Populations for Analyses

The Phase 1 population will include all subjects who receive at least one dose of GC4711. The DLT evaluable population includes all patients in the Phase 1 population who have received all five GC4711 doses, are followed for 30 days post SBRT and were DLT free or experienced a DLT. The Phase 2 intent-to-treat population includes all subjects randomized and is used in disposition. Safety and efficacy analyses for Phase 2 will be performed on a modified intent-to-treat population that includes all randomized subjects who receive at least one dose of GC4711 or placebo.

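### The large-sample 90% interval prescribed in 8.1 and 8.5 covers about one point less than nominal at 30 to 33 patients per arm; Newcombe limits are closer to 90% and narrower

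*Combined protocol and SAP*

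**What the plan says.** Section 8.1 sizes Phase 2 for estimation. It randomises about 66 patients 1:1 "to achieve 60 evaluable subjects, assuming an approximate 9% drop out rate prior to the 90-day timepoint evaluation" and then says: "With 30 patients/arm the half-width of the 90% confidence interval for the difference will be at most 21.2" percent. The interval is the unpooled large-sample one, with limits at plus and minus z times the square root of p1(1-p1)/n + p2(1-p2)/m. Section 8.5 prescribes the same interval for the primary analysis and carries the method over to the secondary response rate. It also says that the study is not powered for formal testing and that P-values are descriptive.

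Section 8.3 runs Phase 2 efficacy analyses on "a modified intent-to-treat population that includes all randomized subjects who receive at least one dose of GC4711 or placebo". Its only definition of an evaluable set is for Phase 1: "The DLT evaluable population includes all patients in the Phase 1 population who have received all five GC4711 doses", with further conditions on follow-up and DLT status. Section 4.4 adds: "In Phase 2, patients who are randomized but do not receive study drug may be replaced". Table 1, footnote e, places randomisation "within 7 days of the first dose of SBRT". Section 3 sets the primary endpoint as best response through Month 6. Table 1 schedules the first post-SBRT tumour CT at Month 6 and none at day 90.

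**The concern.** With no powered test, the confidence interval is the main Phase 2 result and its half-width is the only planning figure. The Wald interval for a difference of two proportions tends to cover less than its nominal level with a few dozen patients per arm, and this can be checked exactly at the planned sizes. An interval labelled 90% that covers somewhat less slightly overstates the certainty passed on to the planning of later studies.

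The planning n is also described in terms that the analysis does not use. Section 8.1 deducts drop-outs up to day 90 to reach an 'evaluable' number. Section 8.3 keeps every dosed patient, whatever happens later, and the endpoint runs to Month 6.

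**Working it through.** **Inputs.** Two-sided 90% level, so z = 1.64485 (8.1, 8.5). Planned n is 30 per arm (8.1). About 33 per arm are randomised (66/2), which is the mITT n if all are dosed (8.3).

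**The plan's own figure.** The Wald half-width is z × √[p1(1-p1)/n + p2(1-p2)/m], largest at p1 = p2 = 0.5, where with equal arms it is z × √(0.5/n).
- n = 30: 1.64485 × √(0.5/30) = 0.2123, or 21.2 points. The stated bound is reproduced.
- n = 33: 1.64485 × √(0.5/33) = 0.2025, or 20.2 points.
- n = 31 and 32 give 20.9 and 20.6.

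**Newcombe limits.** Let l and u be the Wilson limits for each arm and d = p1 - p2. The lower limit is d - √[(p1-l1)² + (u2-p2)²] and the upper is d + √[(u1-p1)² + (p2-l2)²]. Half-width here means half the total width. For 15/30 in both arms, the Wilson half-width is 1.64485 × √(0.25/30 + 1.64485²/(4×30²)) / (1 + 1.64485²/30) = 0.1438. The Newcombe half-width is then √2 × 0.1438 = 0.2034, or 20.3 points. This is the maximum over all outcomes at 30 per arm. At 33 per arm the maximum is 19.5 points.

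**Exact coverage.** For each pair of true rates, sum b(x; n, p1) × b(y; n, p2) over all outcomes (x, y) whose interval contains p1 - p2. Rates run from 0.10 to 0.90 in steps of 0.05, giving 17 × 17 = 289 pairs, of which 179 differ by at most 30 points.

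| Quantity, Wald v Newcombe | 30 per arm | 33 per arm |
|---|---|---|
| Mean coverage, 289 pairs | 88.8% v 89.9% | 88.9% v 89.8% |
| Mean coverage, differences up to 30 points | 89.1% v 89.9% | 89.1% v 89.8% |
| Minimum coverage, differences up to 30 points | 88.0% v 88.0% | 87.7% v 88.8% |
| Mean half-width, 289 pairs (points) | 18.1 v 17.7 | 17.2 v 17.0 |
| Maximum half-width (points) | 21.2 v 20.3 | 20.2 v 19.5 |

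At 31 and 32 per arm, mean coverage over the 289 pairs is 88.6% v 89.9% and 88.6% v 89.7%.

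Section 8.7 plans an interim efficacy look at the first 20 randomised patients. If the same interval were used there with 10 per arm (both are assumptions), mean coverage would be 86.1% v 90.1%.

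**The planning n.** 66 × (1 - 0.09) = 60.06, so the deduction is about 3 of 33 per arm (3/33 = 9.1%). Under 8.3 a dosed patient who later drops out stays in n. Only patients never dosed and not replaced reduce it. With 0 to 3 such patients per arm, n is 33 to 30 and the maximum Wald half-width is 20.2 to 21.2 points.

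**The case against.** The best defence is that nothing here is an error. Sections 8.1 and 8.5 name the same interval, the arithmetic is right, and the coverage shortfall is about one point. For differences up to 30 points the worst case at 30 per arm is no better with Newcombe. The share of rate pairs with coverage below 89% also moves erratically with n (Wald 45%, 65%, 70% and 48% at 30, 31, 32 and 33 per arm), so little weight should rest on it. In addition, 8.5 leaves detail to a statistical analysis plan that will supersede the protocol, and 8.3 already fixes who is analysed. All of this stands, and it makes the point minor. It does not count against the change, because Newcombe is closer to 90% on average at every planned size and gives up no precision.

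A reader might go further and infer from the day-90 clause that losses between day 90 and Month 6 make 21.2 points too optimistic, so that more patients or a Month 6 drop-out allowance are needed. The documents do not support this. Dosed patients stay in the 8.3 denominator, so drop-out after dosing does not reduce n. The bound would be passed (21.6 points at 29 per arm) if the analysis were confined to scanned patients and more than 3 of 33 per arm had no scan, but no section specifies that analysis. A Month 6 allowance would repeat the mismatch with 8.3.

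**Conclusion.** The point holds as a minor improvement. At 30 to 33 per arm the prescribed Wald interval has mean coverage of 88.6% to 88.9%, against 89.7% to 89.9% for Newcombe. For differences up to 30 points the gap narrows to 0.7 to 0.8 point (30 and 33 per arm). The averages weight all rate pairs on the grid equally, because the plan states no expected response rates.

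The 21.2-point bound is correct for Wald. It is conservative because it takes both rates at 50% and 30 per arm, where 8.3 implies up to 33. That assumes no more than 3 patients per arm go undosed without replacement. The 'evaluable' and day-90 wording is a matter of terms: it does not make the bound wrong and gives no reason to change enrolment. The 9% in 8.1 against 10% in the synopsis is rounding.

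**What to change.** In 8.1 and 8.5, replace the Wald limits with Newcombe limits, which also covers the secondary response rate analysed by the same method. In 8.1, state the precision on the 8.3 mITT set: a half-width, defined as half the total width, of at most 20.3 points at 30 per arm and 19.5 at 33. If Wald is kept, the corresponding figures are 21.2 and 20.2.

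In 8.1 and the synopsis, delete 'evaluable' and the drop-out clause (to day 90 in 8.1, with no time point in the synopsis). Plan on the mITT n instead, and note that only patients never dosed and not replaced reduce it. This also removes the 9% and 10% figures.

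The cost is a few sentences and one line of analysis code. Newcombe limits are not symmetric about the estimate, so results must be reported as two limits and not as plus or minus a margin. Enrolment is unchanged and the stated precision does not worsen.
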